## **Cyclooxygenase-2-Inhibitor Combination Treatment for Bipolar Depression: Role of Inflammation and Kynurene Pathway Biomarkers**

### **ABSTRACT**

A chronic sub-threshold pro-inflammatory status may interfere with the ability of an antidepressant to exert its full therapeutic action in bipolar disorder (BPD) patients whose depression has failed to respond or remit. Additionally, a pathological shunt in the kynurene pathway may be involved in these delayed or diminished responses to antidepressant monotherapy.

We propose a placebo-controlled study to treat bipolar depressed patients not responsive to antidepressant monotherapy with the well-known antidepressant escitalopram in combination with the anti-inflammatory agent celecoxib. We hypothesize that combination treatment will result in augmented treatment responses. We also expect to see greater numbers of remitters in response to escitalopram + celecoxib combination therapy compared to escitalopram monotherapy.

### **BACKGROUND**

#### **Burden of Bipolar Depression**

In bipolar disorder I and II, the depressive phase dominates over manic or hypomanic symptoms and most adversely affects the quality of life. In the natural course of bipolar I disorder (BPD), depressive symptoms occur in 31.9% of the weeks, and hypomanic/manic symptoms occur in 8.9% of the weeks the patient experiences symptoms (Judd et al, 2002). In bipolar II disorder, depressive symptoms occur in 50.3% of the weeks and hypomanic/manic symptoms in 1.3% of the weeks (Judd et al, 2003). Amongst 258 bipolar patients admitted from 1996 to 1999 to the Stanley Foundation Bipolar Network, 25% were ill with depressive symptoms averaging 214 days/year and 40% were ill with depressive symptoms averaging 120 days/year (Post et al, 2003a). Despite comprehensive pharmacologic treatment, mean time depressed was 3-fold higher than manic time. 62.8% of patients had 4 or more episodes per year. It was concluded that in bipolar patients' depressive symptoms pose a greater burden for treatment than mania (Post et al, 2003b). The suicide rate is highest in patients with bipolar disorder. It occurs most frequently after severe and recurrent depressive episodes (Tondo et al, 2003). Regarding response to antidepressant treatment, bipolar depressed patients generally respond more poorly than patients with major depression. In a study comparing response to antidepressant treatment of bipolar depressed patients versus that of patients with major depression, the non-response rate was 1.6 times higher in bipolar depressed patients. In another study, failure to respond to anti-depressant therapy was reported to be 3.4 times more common in bipolar depressed patients (Ghaemi et al, 2004). The reasons for the above observations are not clear. However, prompt diagnosis and specific therapeutic strategies are critical for the successful management of bipolar disorder.

#### **Role of Inflammation**

For decades our understanding of the pathophysiology of affective disorders and the development of antidepressant medications have been almost solely guided by the Monoamine Theory of Depression. While monoamine-based antidepressants have proven suitable as a mainstay treatment for most cases, their prolonged intervals to achieve symptom control, and the high percentage of non-remitters in both unipolar and bipolar depression have remained insurmountable attributes of these medications. New and innovative treatment strategies are therefore needed. Meanwhile, there has been an impressive accumulation of knowledge about pro-inflammatory compounds (e.g., cytokines, chemokines, C-reactive protein) contributing to the pathophysiology

of depression. This has led to the formulation of the Cytokine Theory of Depression (Ur et al, 1992; Dantzer et al 2008; Leonard and Song, 1996; Miller et al, 2009). There are numerous reports (Drexhage et al; Drexhage et al; Kim et al, 2007; Kim et al, 2002; Maes et al, 1995; Rapaport et al, 1999; Su et al, 2002; Tsai et al, 1999; Tsai et al, 2001) linking the immune system, in particular cytokines and C-reactive protein (CRP), to bipolar disorder. There is additional evidence that the persistent pro-inflammatory status found in depression may delay, diminish, and even thwart antidepressant response. Furthermore, a persistent pro-inflammatory status is likely increases the risk for depressed patients to develop serious and potentially life-threatening complications such cardiovascular and cerebrovascular disease.

There is an interaction between cytokines and serotonergic transmission involving the metabolism of tryptophan and modulation by the NMDA receptor. This interaction in the CNS occurs in part through the enzyme indoleamine 2,3-dioxygenase (IDO). IDO catabolizes tryptophan to kynurene. Kynurene metabolism has been implicated in the pathophysiology of depression, especially the chronicity of the disorder (Myint and Kim, 2003). The involvement of the NMDA receptor in manic relapse of patients with bipolar I disorder was first proposed by Hoekstra and colleagues (Hoekstra et al, 2006). The up-regulation of the initiating step of the kynurene pathway has been demonstrated in postmortem anterior cingulate cortex from individuals with schizophrenia and bipolar disorder (Miller et al, 2006). A lower plasma tryptophan index, lower neuroprotective kynurenic acid and higher tryptophan breakdown has been observed in bipolar patients compared to controls (Myint et al, 2007a; Myint et al, 2007b). Our unpublished data also indicates that the kynurene/tryptophan ratio in major depression may serve as an indicator of response to add-on treatment with the cyclooxygenase-2 inhibitor, celecoxib.

### **Pro-Inflammatory and Anti-Inflammatory Cytokines**

Endothelial damage leads to the release of pro-inflammatory cytokines, which can induce thrombus formation, vascular occlusion, and have been implicated in the pathogenesis of atherosclerosis and cardiovascular disease (Koenig et al, 2001; McIntyre et al 2007; Piletz et al, 2000). Endothelial damage of the cerebral vasculature is postulated to contribute to the development of an entity referred to as Vascular Depression, which presents with many typical symptoms of depression. Studies have shown that pro-inflammatory cytokines are over-expressed in many stress-related disorders, including depression (Leonard et al, 1999; Tsao et al, 2006; von Kanel et al 2006).

Interestingly, depressed patients with or without cardiovascular disease have been shown to exhibit elevations in pro-inflammatory biomarkers (Dinan et al, 2009; Koenig et al, 2001; Meyer et al 2008). The pro-inflammatory cytokines TNFalpha, IL1beta, and IL6 have consistently been found to be elevated in the plasma of depressed subjects (Himmerich et al, 2006; Tsao et al, 2006; Tulug et al, 2003), and elevated IL-6 concentrations have been associated with an increased prevalence of major depression (O'Brien et al, 2007). Interleukin-6 (IL-6) is secreted in response to stress, induces the release of other pro-inflammatory cytokines and has been implicated in the pathophysiology of MDD and in the effects of antidepressant treatment (Llicino et al, 1999). These observations have led to the postulation that depressive illness is a disease of inflammation in response to chronic psychological stress (Koenig et al, 2001).

### **Anti-Inflammatory Therapy in Depression: Existing Studies with Add-On Celecoxib**

The presence of a pro-inflammatory state in bipolar disorder and the usefulness of anti-inflammatory treatment was the topic of a recent major review article (Berk et al, 2010). There have been 3 clinical studies describing the positive effects of various antidepressant agents with add-on celecoxib therapy. Each study independently concluded that administration of a COX inhibitor enhances the efficacy of the antidepressant. In some instances

non-responders remitted. All studies underscore the safety of celecoxib when used in doses up to 400 mg/day for 8 weeks.

Study No. 1: In a double-blind, randomized, placebo-controlled study, celecoxib + reboxetine was administered to MDD patients to determine if 6 weeks of combination therapy would result in improved outcomes as compared to reboxetine monotherapy. Celecoxib was titrated from 200 mg/d to 400mg/d over 3 days. Subjects receiving reboxetine + celecoxib showed a significantly greater antidepressant response by week-5 than subjects on reboxetine + placebo. Safety issues were assessed by self-reporting. No laboratory measurements were performed to assess hematologic or cardiovascular issues that might have arisen with drug combination. Mueller et al, 2006.

Study No. 2: In a double-blind, randomized, placebo-controlled study, add-on celecoxib or placebo was administered for 6 weeks to non-responsive bipolar patients experiencing depressive or mixed episodes while maintained on stable doses of multiple mood stabilizers, atypical antipsychotics, antidepressants, and benzodiazepines. A statistically significant improvement ( $p=0.03$ ) was noted in the first week of treatment with add-on celecoxib in those who completed treatment. This pilot study was limited by small numbers ( $n=23$  for completers). The study did not measure drug levels or inflammation biomarkers. The overall finding was a better outcome in patients treated with celecoxib add-on. Nery et al, 2008.

Study No. 3: In a double-blind, randomized, placebo-controlled study, 40 acutely depressed MDD subjects were treated with fluoxetine + placebo or fluoxetine + celecoxib for 6 weeks. At 6 weeks of treatment, patients receiving combination therapy showed statistically more improvement than patients receiving monotherapy. The celecoxib add-on was well-tolerated in study patients. Plasma levels of fluoxetine were monitored and no significant drug-drug interactions in metabolism were noted. No inflammation biomarkers were measured. Akhondzadeh et al, 2009.

### Using Celecoxib Instead of Another NSAID

There are more preliminary reports using CBX as an add-on treatment for depression than any other add-on NSAID strategy. Additionally, as a COX-2 inhibitor CBX lacks the substantive anti-platelet effects associated with other NSAIDs on the US market which are non-selective mixed COX-1/COX-2 inhibitors, such as aspirin (Riondino et al, 2008). Using CBX allows for reasonable confidence that changes (i.e., in biomarkers) could not result from indirect effects on platelets or coagulation. Furthermore, due to pharmacokinetic reasons the analgesic effects of CBX take effect slower than other NSAIDs. Having a 3-hour interval between medication ingestion and effect onset decreased the likeliness that a cue can be perceived by the patient, thereby breaking the blind.

In addition to these pharmacological issues, the use of CBX also rests on basic science findings linking COX-2 up-regulation to depression. Pro-inflammatory cytokines are known to activate the HPA axis and exert profound effects on central monoaminergic transmission (Benedovsky et al, 1991), and at least three of them (IL-1 $\beta$ , IL-6 and TNF $\alpha$ ) are acted upon by COXs. While there are multiple isoforms of COXs, the main focus of the field has been on COX-2 because it is the isoform that is cytokine-induced through NF $\kappa$ B-dependent mode (Funakoshi-Tago et al, 2008). Stressors such as depression up-regulate transcription factor NF $\kappa$ B, which is mediator of pro-inflammatory cytokines in monocytes (Miller et al, 2009). Moreover, the predominant reaction of COX-2 is conversion of arachidonic acid to prostaglandin E2 (PGE2). Increased PGE2 in saliva, serum, and CSF of depressed patients has previously been described (Lieb et al, 1983; Calabrese et al, 1986). Since PGE2 stimulates IL-6 release, it seems likely that some of the changes observed in depression with IL-6 may be related to the COX-2 pathway.

The up-regulation of PGE2 has also been described in response to different physical, psychological, or mixed trauma experimental paradigms like social crowding, immobilization, or cold restraint stress in animals.

Furthermore, there is evidence that up-regulation of COX-2 can enhance glutamatergic neurotransmission. Sang (2007) demonstrated that PGE2 glyceryl ester (PGE2-G), a major COX-2 oxidative metabolite of 2-arachidonoyl-glycerol, enhances hippocampal glutamatergic synaptic transmission, inducing neuronal injury and death. This supports the fact that COX-2 has also been implicated in the pathogenesis of neurodegenerative disorders such as Parkinsonism, Multiple Sclerosis, Alzheimer's disease and traumatic brain injury. According to contemporary theories, depressive states are also neurodegenerative (Lieb et al, 1983; Calabrese et al, 1986; Yang et al, 2008). Taken together, there is a strong body of literature suggesting that COX-2 up-regulation in depression may pose a serious risk not only for the mood disorder itself, but also for the emergence of neurodegeneration at later time points in life.

### **Pro-Inflammatory Biomarkers: Anticipated Effect of Celecoxib Add-On**

CBX inhibits COX-2 and its end-products (i.e. PGE2). Funakoshi-Tago et al. (2008) demonstrated that CBX significantly inhibits TNF $\alpha$ -induced NF-kappaB activation by preventing the nuclear translocation of the p65 NF-kappaB subunit. In a study of patients with osteoarthritis randomized to either CBX or aceclofenac, CBX potently inhibited PGE2 concentrations and down-regulated both COX-2 mRNA and protein expression at the synovial membrane (Alvarez-Soria et al, 2006). In a double-blind, placebo-controlled, crossover trial of CBX (200 mg BID) of patients with severe coronary artery disease undergoing stable background therapy with aspirin and statins, 2 weeks of treatment with CBX led to a marked reduction in two pro-inflammatory agents: CRP and oxidized LDL (Chenevard et al, 2003). Muller et al (2004) used add-on CBX (400 mg/d) with an antipsychotic, risperidone. Their study monitored soluble TNF $\alpha$  receptor levels before and during 5 weeks of treatment. CBX add-on led to significantly better-than-placebo responses in the total PANSS scores for schizophrenia improvement at weeks 2, 3, and 4 (Leonard et al, 1999). Finally, there are no major drug-drug interactions expected between CBX and ESC based on having common cytochrome P450 enzymes.

### **Pro-Inflammatory Biomarkers: Predictive Value with Respect to Antidepressant Response**

Studies indicate that plasma levels of pro-inflammatory biomarkers could be predictive of treatment response or non-response. Lanquillon et al (2000) studied MDD inpatients before and after treatment with amitriptyline. Untreated MDD patients had overall higher levels of plasma CRP, TNF $\alpha$ , and IL6 than control patients. MDD patients fell into three groups during treatment: responders, non-responders, and drop-outs. Non-responders had the highest IL-6 values before treatment.

O'Brien et al (2007) compared patients at the end of a failed 6-week trial on an SSRI with patients who had previously failed an SSRI but were euthymic at time of blood drawing (due to switch to venlafaxine or SSRI augmentation with lithium). This study found SSRI-resistant patients have significantly higher levels of TNF $\alpha$  and IL6 compared to euthymic treatment responders.

Yoshimura et al (2009) compared TNF $\alpha$  and IL6 levels before and after treatment in antidepressant treatment responders and non-responders. High IL6 levels before and after treatment was indicative of non-responders, regardless of the agent used.

After 6 weeks of SSRI treatment, Dinan et al (2009) divided depressed patients into two groups: SSRI non-responders and SSRI-responders. Omega-3 fatty acid, eicosapentanoic acid (EPA) was shown to be a state marker. EPA competes with arachidonic acid (AA) as a substrate for cyclooxygenase-2 (COX-2). These studies

provide evidence that pro-inflammatory biomarkers may be clinically useful in predicting antidepressant response.

### **Genetic Testing**

The association between depressive disease and serotonergic transmission is well established. Similarly, there is a compelling link between depression and risk for developing cardiovascular disease. Abnormalities of serotonergic mechanisms in depression have been described and reviewed (Leonard 2000 and Mendelson 2000) in the literature over the past decades. Studies have reported decreased platelet aggregation in response to serotonin, but Shimbo et al. (202) reported a significant increase in platelet reactivity to serotonin in depressed patients. Whyte et al. (2001) demonstrated that depressed patients with the serotonin-transporter-linked promoter region 1/1 genotype have increased platelet activation compared to both depressed patients without this genotype and non-depressed control subjects. These authors hypothesize that persons with this polymorphism are likely to experience higher mortality rates. More recent evidence shows that certain pro-inflammatory cytokines (e.g, TNFalpha, IL-6) reduce serotonergic transmission by inducing the enzyme indoleamine dioxygenase (IDO) and shunting tryptophan away from the synthesis of serotonin. Taken together, these findings strongly indicate that genotyping could be used to identify patients at greater risk of developing depression and depression-associated cardiovascular morbidity and mortality (White et al., 2001).

### **Salivary Cortisol Testing**

Recent evidence suggests that a prolonged inflammatory response can lead to dysregulation of the hypothalamic-pituitary-adrenal axis, potentially due to pro-inflammatory modulators such as TNF-a and IL-6 (Straub et. al, 2011). HPA axis dysfunction has the potential to lead to an overall increase in secretion of cortisol and disruption of the well-established diurnal rhythm of cortisol, a glucocorticoid released in response to stress (Zunszain et. al, 2011). Evidence suggests that variation of the HPA axis and subsequent alterations in cortisol levels may be associated with the depressive phase in bipolar patients (Van der Werf-Eldering et. al, 2012). Obtaining cortisol through salivary collection has shown to be an effective, non-invasive method for evaluating the HPA axis, and research shows that there is a strong correlation between salivary and blood levels of cortisol (Marques et. al, 2010).

## **HYPOTHESES AND SPECIFIC AIMS**

**HYPOTHESIS:** The pro-inflammatory state of BPD subjects can delay, diminish or even thwart antidepressant monotherapy. Combination therapy of escitalopram + celecoxib will result in improved treatment outcomes (faster action, augmented response, and/or higher remission rates) for treatment-resistant BPD subjects. Response to antidepressant treatment in BPD subjects will be proportional to the change in pro-inflammatory status before and after treatment.

**SPECIFIC AIM #1:** Determine if combined pharmacotherapy of escitalopram + celecoxib will result in improved affective responses compared to escitalopram + placebo. Scores from the Short-Form McGill Pain Inventory will be used to control for variation in depression that could be attributed to the relief of physical pain resulting from administration of celecoxib.

**SPECIFIC AIM #2:** Determine whether combined pharmacotherapy of escitalopram + celecoxib causes any pharmacokinetic drug-drug interaction or poses safety/tolerability issues in terms of gastrointestinal bleeding or cardiovascular health. Clinical and laboratory assessments will be made throughout treatment and an adverse events inventory will be completed at each visit.

**SPECIFIC AIM #3:** Determine the blood concentration of pro-inflammatory biomarkers of all subjects before and after treatment. Determine whether there is a correlation between blood concentration of pro-inflammatory biomarkers and the psychiatric effectiveness of the combined treatment.

**SPECIFIC AIM #4:** Quantify the specific anti-inflammatory action of celecoxib by assaying for inhibition of PGE2. PGE2 concentrations will be measured from the blood of all subjects before and after treatment.

**HYPOTHESIS:** A chronic pro-inflammatory state leads to endothelial dysfunction, arterial stiffness, and dis-regulation of the autonomic nervous system with sustained sympathetic activation and diminished vagal tone.

**SPECIFIC AIM #5:** Determine whether endothelial dysfunction is present in BPD subjects and if this dysfunction will respond favorably to the combined treatment of escitalopram + celecoxib. The detection will be accomplished by means of arterial pulse wave analysis, velocity and heart rate velocity.

**HYPOTHESIS:** A pathological shunt in the kynurenine pathway exists in BPD patients who fail to remit on antidepressant treatment. This shunt interferes with the ability of an antidepressant agent to exert its full therapeutic action.

**SPECIFIC AIM #6:** Determine the nature of the kynurenine pathway in all subjects before and after treatment.

**HYPOTHESIS:** A genetic polymorphism identified in the 5-HT-transporter-linked promoter region may predispose subjects to depression and associated cardiovascular risk.

**SPECIFIC AIM #7:** Genotype the serotonin transporter length polymorphic region (5-HTTLPR) on all subjects to determine if the 5HTTLPR alleles associate with bipolar depression, inflammation biomarkers, heart rate variability and endothelial dysfunction.

## **STUDY ENDPOINTS**

The primary endpoints pertain to the main hypothesized outcome: namely, a significantly better-than-placebo mood response for escitalopram + celecoxib that is not related to altered pain perception.

The HAM-D rating scale (17 items from the 21-item scale) will be the main measure of clinical improvement. Onset of response is defined as the day of treatment when a 30% decline in the initial (day 0) HAM-D score is recorded and is maintained for two consecutive weeks. Treatment response is defined as a 50% reduction in the initial HAM-D score occurs. Symptom remission is defined as a HAM-D score of 7 or less.

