### **I. Primary Endpoint**

We seek to establish whether the combination therapy of escitalopram + celecoxib will augment antidepressant efficacy compared to escitalopram therapy alone as demonstrated by:

- a significantly earlier group response (earlier decline in HAM-D scores)
- a more robust group improvement in HAM-D scores at 8 weeks of treatment
- more patients with symptom remission than in the escitalopram + placebo group at 8 weeks

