At the Baseline visit, subjects will be reassessed for depression and associated symptoms. If subjects continue to score 18 or higher on the 17-item HAM-D scale, they will be randomized to receive escitalopram + celecoxib, or escitalopram + placebo in an assignment ratio 1:1. Subjects will then go on to complete assessments at Week 1, Week 2, Week 4 and Week 8. If the subject scores below 18 on the 17-item HAM-D scale at Baseline, he or she will be terminated from the study and classified as a placebo responder. At each of these visits, subjects will arrive 30 minutes before their scheduled appointment time, rest for 20 minutes in the exam room, and provide a saliva sample prior to undergoing any assessments. Terminated subjects will be offered conventional care at the same institution.

It is our desire to observe the diurnal nature of cortisol levels in saliva by measuring the patient's salivary cortisol levels at a time point prior to treatment and post treatment. At each of these two time points, we would collect saliva from the patient at five times during the day: upon awakening, approximately 30 minutes past awakening, before lunch, at approximately 3pm, and before bedtime. The patient would be required to do this at home and would then store the samples in their refrigerator until their next visit. Subjects will be provided with a log to record the exact time of saliva collection. We will be using salivettes purchased from Sarstedt Inc., and our Salivary Assay kits will be purchased from Salimetrics, LLC.

The overall study is powered for 90 subjects. We aim to randomize 70 subjects at LUMC. Approximately 30 subjects will be randomized by investigators at our sister site in Munich, Germany. At LUMC, 35 subjects will be randomized to each arm of the study. Subjects must complete 8 weeks of active medication to be considered study completers. We plan to enroll approximately 80 patients in anticipation of a 10% drop-out rate. The drop-out rate is based on our experience with our patient population over the past 5 years. If a subject drops out or is terminated after Week 6, their last observation will be carried forward in the analysis (LOCF). There are no healthy controls in this study because we already possess normative, untreated data for comparison.

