## STUDY PROCEDURES

### Schedule of Events

Procedure	Screen 1	Screen 2	Baseline	Week 1	Week 2	Week 4	Week 8
Consent	X						
Assign Subject ID	X						
MINI	X						
HAM-D/HAM-A/MADRS	X*	X*	X	X	X	X	X
CGI/CSSRS/AdverseEvents/CSULGIE	X		X	X	X	X	X
Self-Assessment Packet			X	X	X	X	X
Dispense Study Medication		PBO	X	X	X	X	X
Physical Exam	X						X
Drug Screen and Pregnancy Test	X						X
Routine Clinical Labs	X						X
Research Blood Draw			X			X	X
CBC/PT/PTT Monitoring	X				X	X	X
Pulse Wave Analysis			X			X	X

Heart Rate Variability			X			X
Albuterol Challenge			X			X
Pulse Wave Velocity			X			X
Saliva Sampling		X	X	X	X	X

\*HAM-D only.

Routine Clinical Labs include complete blood count, complete metabolic panel, lipid profile and thyroid function.

The following assessments are included in the self-assessment packet:

- Beck Depression Inventory (BDI)
- Beck Anxiety Inventory (BAI)
- State/Trait Anxiety Inventory (STAI)
- Spielberger Anger Expression Inventory (STAXI)
- International Physical Activity Questionnaire (I-PAQ)
- Quality of Life and Enjoyment Questionnaire (QLES-Q)
- The Short-Form McGill Pain Inventory (MPI)
- Perceived Stress Scale (PSS-14)

Subjects will be treated as outpatients for a total of ten weeks. Subjects must complete at least six weeks to be regarded as completers. If a subject chooses to withdraw from the study on or after six weeks of treatment, he or she will be asked to complete end-of-study assessments at that time. Those results will be carried forward for the purpose of data analysis.

Subjects will not receive any other type of therapeutic intervention (e.g., psychotherapy) during participation in the study. Such options may be offered to them at the conclusion of the study, if appropriate.

Subjects who complete the study and respond favorably will remain under the care of the LUMC physician, if they wish.

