## DATA ANALYSIS AND STATISTICAL METHODS

### I. Statistical Analysis

Specific Aim 1 is to determine if combined pharmacotherapy of escitalopram + celecoxib will result in earlier and/or improved affective responses compared to escitalopram + PBO. Additionally, Specific Aim 1 seeks to control for pain perception in this analysis. For this aim, the patients in the two treatment arms will be compared on HAM-D, HAM-A, MADRS, BDI, and BAI scores. This will be accomplished with an analysis of covariance conducted at weeks 1, 2, 4 and 8. Baseline mood scores and McGill Pain Inventory scores will be used as covariates. In addition, the number of patients who are and are not classified as remitters at week 8 (those having a HAM-D score of 7 or less) will be tallied and cross-referenced with treatment group (escitalopram + celecoxib or escitalopram + PBO). The frequencies in the resulting 2-by-2 contingency table will be analyzed with the Pearson Chi-Square Test for Association.

For Specific Aim 2, dealing with treatment safety and tolerability, the numbers of patients who do and do not experience adverse events at weeks 1, 2, 4, and 8 will be tallied and cross-referenced with treatment group. The frequencies in the resulting 2-by-2 contingency table will be analyzed with the Pearson Chi-Square Test for Association. Additionally, to understand whether any pharmacodynamic interaction exists between escitalopram and celecoxib, blood levels of escitalopram and celecoxib drawn at weeks 4 and 8 will be compared for patients in the two treatment groups with an analysis of covariance using baseline levels as a covariate. If there is no pharmacokinetic interaction then we expect that there will be no statistically significant results for these analyses.

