## II. Determination of Sample Size

Although a number of tests of statistical significance are planned for the proposed study, our required sample size is being based upon the primary outcome of treatment effect (Specific Aims 1). In looking at differences in mean HAM-D scores from the studies by Akhondzadeh et al. 5 and Mueller et al. 6 we found that the effect sizes of an antidepressant + anti-inflammatory agent over an antidepressant + placebo at week 3 of treatment were 0.53 and 0.52, respectively. In the proposed research we anticipate that the effect size will be slightly higher due to the fact that variation in depression scores attributable to baseline levels and pain perception will be eliminated in an analysis of covariance. Hence, we anticipate that the effect size will be about 0.60 for escitalopram + celecoxib over escitalopram + PBO. As noted earlier, we anticipate that the drug combination will lead to a therapeutic response that is earlier than what is normally seen at week-3 of treatment. We thus expect to see a treatment effect at week-2 of therapy, and expect that the magnitude of the effect will increase over the course of the study. The increasing separation between the different treatment groups is similar to what was found in the studies mentioned above which observed rising treatment effects during the course of therapy. From this, our computations indicate that a sample size of 45 patients per group will provide 80% power for an analysis of covariance to detect an effect size of 0.60 at week-2 of therapy using a 0.05 level of significance. Thus, a total of 90 patients completing treatment will be acquired for the proposed work. 30 of the total patients will be enrolled and randomized at our sister site in Munich, Germany. Given that the therapeutic effect size is expected to increase over time, the proposed sample size will be adequate throughout the course of the study. Subjects lost to attrition will be replaced.

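### The onset-of-response definition is only partly checkable at the scheduled visits and no analysis uses it, and the plan does not say which visit's ANCOVA decides the first primary endpoint, earlier response

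*Combined protocol and SAP*

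**What the plan says.** Study Endpoints makes the 17-item HAM-D the main measure and defines three patient-level states: onset, response (a 50% reduction) and remission (a score of 7 or less). Onset is the treatment day on which "a 30% decline in the initial (day 0) HAM-D score is recorded and is maintained for two consecutive weeks".

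Study Design fixes the ratings after randomisation: "Subjects will then go on to complete assessments at Week 1, Week 2, Week 4 and Week 8". The Schedule of Events agrees. It adds one unscheduled possibility: for a patient who withdraws at six weeks or later, "he or she will be asked to complete end-of-study assessments at that time".

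Section I, Primary Endpoint, has three bullets. The first is "a significantly earlier group response (earlier decline in HAM-D scores", with the bracket closing there. The other two are greater improvement at 8 weeks and more remitters at 8 weeks.

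Section I, Statistical Analysis, restates Specific Aim 1 as whether the combination "will result in earlier and/or improved affective responses compared to escitalopram + PBO". For the mood scores, "This will be accomplished with an analysis of covariance conducted at weeks 1, 2, 4 and 8", with baseline mood and McGill pain scores as covariates. The only categorical efficacy test cross-tabulates treatment with "the number of patients who are and are not classified as remitters at week 8". Each test uses a 0.05 level, and any adjustment for the number of tests is left to a later stage.

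Section II, Determination of Sample Size, says that the treatment effect is expected by week 2. Its power statement refers to that week: "a sample size of 45 patients per group will provide 80% power for an analysis of covariance to detect an effect size of 0.60".

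**The concern.** Two gaps meet here. First, the onset rule asks for a dated event and a two-week hold, while the visits are one, two and four weeks apart. For some patients the hold cannot be observed as defined, and the plan gives no rule for classifying them. Two analysts could assign different onset status to the same data.

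Second, the definition leads nowhere. It stands in the endpoint section beside a primary endpoint about earlier response, but the analysis section contains no time-to-onset test, no comparison of onset proportions and no censoring rule. What remains for the earlier-response claim is a series of unranked ANCOVAs. At stake is the first-listed primary claim: as written, a significant difference at week 1, week 2 or week 4 could each be presented as showing it.

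**Working it through.** **Step 1. The plan's own sample size.** Inputs from Section II, Determination of Sample Size: effect size d = 0.60, level 0.05, power 80%, 45 per group. The plan does not state sidedness; two-sided is assumed.

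- Normal approximation: n = 2 × (1.960 + 0.842)² / 0.60² = 43.6, so 44 per group.
- Two-sample t test: n = 44.6, so 45 per group; power at 45 is 80.4%.
- ANCOVA F test with two covariates at n = 45: noncentrality (45/2) × 0.36 = 8.1 on 1 and 86 degrees of freedom; power 80.3%.
- A one-sided test would need 35 per group, which does not match.

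The stated figure reproduces. It concerns mean HAM-D at week 2, not time to onset.

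**Step 2. Can the two-week hold be checked?** For onset first recorded at week w, the window runs to week w + 2.

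| Onset first seen | Window ends | Scheduled rating inside window | Next rating at or after its end |
|---|---|---|---|
| Week 1 | Week 3 | Week 2 | Week 4 |
| Week 2 | Week 4 | Week 4 | Week 4 |
| Week 4 | Week 6 | none | Week 8 |
| Week 8 | Week 10 | none | none |

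Two of the four possible onset visits can be checked at one point or more. The other two cannot be checked as defined. The withdrawal assessment could fall inside the week-4 window only for a patient who leaves at week 6 itself. The recorded onset day can only be about day 7, 14, 28 or 56. The true day is known only to the preceding interval, which is two weeks wide before week 4 and four weeks wide before week 8.

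**Step 3. Does any analysis use the definition?** Setting the endpoint section against the two statistical sections:

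- Earlier response: ANCOVA of scores at weeks 1, 2, 4 and 8. No deciding visit is named.
- Improvement at week 8: ANCOVA at week 8.
- Remission at week 8: Pearson chi-square.
- Onset (30% decline, held): no analysis.

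**Step 4. Size of the open choice.** Suppose there is no treatment effect and a HAM-D ANCOVA significant at any of weeks 1, 2 or 4 would be taken as earlier response. The documents give no between-visit correlation, so equal correlations r of 0.5 to 0.8 between the three test statistics are assumed. Write each statistic as √r·U + √(1−r)·e, with U and e independent standard normals. With c = 1.960,

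P(at least one significant) = 1 − ∫ φ(u) [Φ((c − √r·u)/√(1−r)) − Φ((−c − √r·u)/√(1−r))]³ du.

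- r = 0.5: 12.5%.
- r = 0.8: 9.8%.
- Reference limits: 1 − 0.95³ = 14.3% for independent tests, 5% for perfectly correlated ones.

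These count differences in either direction. Counting only differences that favour celecoxib (at least one statistic above 1.960), the same model gives 6.3% at r = 0.5 and 4.9% at r = 0.8, against 2.5% for a single test.

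**The case against.** Three stronger readings are tempting, and the documents support none of them.

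- *The two-week hold can never be verified.* It can be, in part. Week-1 onset is rated again at weeks 2 and 4, and week-2 onset exactly two weeks later. These are the visits that matter most for a claim of early response. The rule does not demand a rating on exactly the fourteenth day after onset. Any sustained-response rule leaves a decline first seen at the last visit unconfirmed, so the week-8 gap alone is no special fault of this protocol.
- *The first primary endpoint has no test.* Its own bracketed explanation is an earlier decline in scores at group level, and the early ANCOVAs compare exactly that. It is the onset definition that goes unused.
- *The claim will be decided by whichever early ANCOVA succeeds.* The plan does not say so. The sample-size section singles out week 2 in advance and ties it to the expectation of early action. It stops short of making week 2 the deciding test.

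Two further points have force. Because no analysis uses onset, misclassifying it cannot change any planned result, and response and remission are defined separately. The study also calls itself proof-of-concept and exploratory, which softens any complaint about multiplicity. What stands is that the definition has no role, that it cannot be applied as written at two of four visits, and that the deciding visit for a primary endpoint is unnamed.

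**Conclusion.** The point holds at moderate weight. The onset definition is checkable for onset first seen at weeks 1 and 2, not within its own window for week 4, and not at all for week 8. It is dated only to a visit interval and feeds no planned analysis. Earlier response is tested by ANCOVA of scores, but with the deciding visit left open.

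The cost of leaving it open is a false-positive chance of about 10% to 13% instead of 5% for the first-listed primary claim. That range assumes no true effect, equal correlations of 0.5 to 0.8, two-sided tests, and that any one of weeks 1, 2 and 4 would be accepted as proof. It covers the HAM-D alone; the same ANCOVAs are planned for four other scales. The documents allow such a choice but do not announce it, so the figure measures an ambiguity and not a stated rule.

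**What to change.** In Section I, Statistical Analysis, name the week-2 HAM-D ANCOVA, with the covariates already planned, as the single confirmatory test of earlier response. State that the week-1 and week-4 contrasts are descriptive. This matches the existing sample-size calculation. The week-8 ANCOVA and the remission test keep their present roles for the other two primary bullets; how those are weighed together is a separate question that this change does not settle.

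In Study Endpoints, either delete the onset definition or restate it in scheduled visits, for example a 30% decline still present at the next scheduled visit, with declines first seen at week 8 reported as unconfirmed. Keep it descriptive. Such a rule means a hold of one week for onset at week 1, two weeks at week 2 and four weeks at week 4. Confirmation is then easier the earlier onset is seen, so it is a poor basis for a confirmatory comparison. A survival model for onset is possible but not needed, and the documents give no onset rate from which to judge its power.

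The cost is protocol and SAP wording, with no new visits, patients or data, provided it is settled before unblinding. The downside is real: a difference seen only at week 1 or only at week 4 could no longer support the earlier-response claim.
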